5.3.1.1 Immediate

For unsolicited non-serious systemic AEs, a missing response to the “Immediate” field is assumed to have occurred after the 30-minute surveillance period and will not be imputed.

For SAEs, missing or partially missing elapsed time from last vaccination recorded if within 24 hours will be assumed to have occurred after the 30-minute surveillance period and will not be imputed. Such SAEs will not be considered as immediate.

5.3.1.2 Causality

Missing causality (relationship) for unsolicited non-serious AEs and SAEs will be considered at the time of analysis as related to vaccination.

5.3.1.3 Measurements

Partially missing temperatures will be handled as described in [Section 4.4.1.1.1](#).

5.3.1.4 Intensity

For solicited reactions, missing intensities will be handled as described in [Section 4.4.1.1.1](#). For unsolicited non-serious AEs, missing intensities will remain missing and will not be imputed.

5.3.1.5 Start Date and Stop Date

Missing or partially missing start dates for unsolicited AEs will remain missing and not be imputed. If either the start or stop date is missing or partially missing, the time of onset will be considered to be missing. Nevertheless unsolicited AEs with missing time of onset will be included in analyses according to the visit collected.

Missing or partially missing stop dates for AEs (solicited reactions and unsolicited AEs) will remain missing and not be imputed.

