4.4.1.2.3 Last Vaccination

Last vaccination before any unsolicited non-serious AE is the study vaccination at V01.

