4.4.1.2.4 Time of Onset

Time of onset is derived from the start date of the unsolicited non-serious AE provided in the clinical database and the date of last vaccination:

- start date of the unsolicited non-serious AE – date of previous vaccination

The time of onset should be considered as missing only if one or both of the dates are missing or partially missing.

The unsolicited non-serious AEs will be analyzed “Within 30 days”, which corresponds to AEs with a time of onset between 0 and 30 days after vaccination or missing. An AE with missing time of onset will be considered to have occurred just after the vaccination indicated by the visit number, so will be included in these tables.

Note: Unsolicited non-serious AEs that occurred before vaccination (negative time of onset) or with a time of onset higher than defined above will not be included in analysis, but will be listed separately.

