4.4.1.2.5 Duration

Duration is derived from the start and stop dates of the unsolicited non-serious AE provided in the clinical database:

- stop date of unsolicited non-serious AE - start date of unsolicited non-serious AE + 1.

The duration should be considered as missing only if one or both of the start and stop dates of the unsolicited non-serious AE is missing or partially missing.

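### SAP Section 5.3.1.5 sets time of onset to missing when only the stop date is missing, which contradicts the derivation in Section 4.4.1.2.4

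*SAP*

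**What the plan says.** The SAP gives two rules for when time of onset is missing.

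- **Section 4.4.1.2.4** derives onset as "start date of the unsolicited non-serious AE – date of previous vaccination" and then states: "The time of onset should be considered as missing only if one or both of the dates are missing or partially missing". The two dates meant are the AE start date and the vaccination date; the stop date is not an input.
- **Section 5.3.1.5**, under the handling of missing data, states: "If either the start or stop date is missing or partially missing, the time of onset will be considered to be missing". It continues: "Nevertheless unsolicited AEs with missing time of onset will be included in analyses according to the visit collected".

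Three further rules determine what follows.

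- Section 4.4.1.2.4 defines the 30-day analysis as one "which corresponds to AEs with a time of onset between 0 and 30 days after vaccination or missing". Its note says that AEs starting before vaccination "or with a time of onset higher than defined above will not be included in analysis"; they are listed separately.
- Section 4.4.1.2.3 fixes a single reference vaccination: "Last vaccination before any unsolicited non-serious AE is the study vaccination at V01".
- Section 4.4.1.2.5 uses the start/stop condition for a different variable: "The duration should be considered as missing only if one or both of the start and stop dates" is missing or partial.

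**The concern.** A derived variable should have one rule, and here the two cannot both be followed. The triggering record is one the SAP expects. The footnote on stop dates in Section 4.3.2.3.3 treats an AE with no stop date as ongoing at the end of the trial, and Section 5.3.1.5 leaves missing stop dates unimputed. An ongoing AE with a fully known start date has an onset day under 4.4.1.2.4 and none under 5.3.1.5.

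If 5.3.1.5 is the rule programmed, two things follow for unsolicited non-serious AEs.

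1. Ongoing AEs that began on D0 to D30 stay in the tables but lose a known onset day. Time of onset is a declared safety endpoint in Section 4.3.2.2.
2. Ongoing AEs that began after D30 and before Visit 2 enter the 30-day tables, although the note in 4.4.1.2.4 keeps them out. Such AEs can be recorded, because Section 3.1 collects unsolicited AEs to Visit 2, which may be as late as D44.

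**Working it through.** **The two rules applied to the same records.** Vaccination is on D0, the start date is complete and the stop date is missing.

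| AE start | Section 4.4.1.2.4 | Section 5.3.1.5 |
|---|---|---|
| D5 | Onset 5, in the 30-day table | Onset missing; still in the table, onset day lost |
| D35, Visit 2 at D40 | Onset 35, listed only | Onset missing, so counted in the 30-day table |
| Before vaccination | Negative onset, listed only | Onset missing, so counted in the 30-day table |

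The third row is a narrow route, because consent and vaccination both take place at Visit 1 (Table 3.2). For membership of the 30-day tables, the 5.3.1.5 rule can only add AEs and never removes one.

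**Does the visit rule in 5.3.1.5 prevent the second row?** Not clearly. There is one vaccination, at Visit 1, and 4.4.1.2.4 attaches a missing-onset AE to the vaccination indicated by its visit number. An AE collected up to Visit 2 therefore still belongs to that vaccination.

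**Exposed days, from the SAP's visit window.** The days after D30 on which an AE can start and still be collected are:

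- Visit 2 at D30: 0 of 31 days.
- Visit 2 at D37: 7 of the 38 days D0 to D37, 7/38 = 18.4%.
- Visit 2 at D44: 14 of the 45 days D0 to D44, 14/45 = 31.1%.

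**One subject wrongly added**, with no other event in the table: 1/500 = 0.20 points at the planned group size (Section 3.1). If the safety set held 450 per group (an assumption), 1/450 = 0.22 points.

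**Illustration per group of 500.** The SAP gives neither AE rates nor the frequency of missing stop dates, so these inputs are assumed: a share p of subjects, 20% to 40%, with one unsolicited non-serious AE in the 31 days D0 to D30; a uniform onset rate that continues after D30; and a share q of AEs, 2% to 10%, without a complete stop date. Let d be the number of collected days after D30.

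- AEs losing a known onset day = 500 × p × q
  - p = 0.2, q = 0.02: 500 × 0.2 × 0.02 = 2
  - p = 0.4, q = 0.10: 500 × 0.4 × 0.10 = 20
- Subjects wrongly added = 500 × p × (d/31) × q × (1 − p), where the last factor keeps only subjects with no AE already counted
  - d = 7, p = 0.2, q = 0.02: 500 × 0.2 × (7/31) × 0.02 × 0.8 = 0.36 (0.07 points)
  - d = 7, p = 0.4, q = 0.10: 500 × 0.4 × (7/31) × 0.10 × 0.6 = 2.71 (0.54 points)
  - d = 14, p = 0.4, q = 0.10: 500 × 0.4 × (14/31) × 0.10 × 0.6 = 5.42 (1.08 points)
  - d = 0: 0

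**The case against.** The best reply is that 4.4.1.2.4 is plainly the operative rule. It sits with the calculation methods and gives a formula with no stop-date term. The SAE and MAAE sections (4.4.1.3.2 and 4.4.1.4) refer to it or its parent section, and nothing sends the onset derivation to 5.3.1.5. The start/stop wording matches the duration rule, so 5.3.1.5 looks like a drafting slip. A programmer who follows 4.4.1.2.4 cannot produce the error.

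Wrong inclusion also needs several conditions together: Visit 2 after D30, a start in the days between, a stop date still incomplete at analysis, and, to move a subject percentage, no other counted event. Stop dates can be supplied throughout the trial and those of related AEs are actively sought (Section 4.3.2.3.3), so missing ones should fall mainly on events judged not related. That section also asks parents to record events over 30 days, so recording after D30 may be less complete than the illustration assumes.

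Most of this stands, and it lowers both the likelihood and the size of the effect. It does not remove the conflict. The SAP states no precedence, and a programmer with an incomplete date would naturally look in the missing-data section, where the wrong rule is.

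**Conclusion.** The contradiction is certain, and Section 5.3.1.5 is wrong as written: it discards known start dates and can bring into the 30-day tables AEs that 4.4.1.2.4 excludes. Whether any output is affected depends on which section is programmed; under 4.4.1.2.4 nothing goes wrong.

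The size cannot be derived from the SAP and is probably small. The illustrated range for wrong inclusion runs from none, with every Visit 2 at D30, to about 5.4 subjects per group. That upper end needs every Visit 2 at D44 together with the top of both assumed ranges. The figures show scale and are not estimates.

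The reach is limited to descriptive tables of unsolicited non-serious AEs. The same rule applies to both groups, and no hypothesis test or immunogenicity result is touched. No effect on SAEs is claimed: Section 4.4.1.3.2 takes SAE onset from 4.4.1.2.4, and Section 5.3.1.2 shows that the SAP names SAEs where it means them. The point should be fixed because a declared safety endpoint has two incompatible definitions.

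**What to change.** Replace the conflicting sentence in Section 5.3.1.5 with one to this effect: *Time of onset is missing if the start date or the vaccination date is missing or partial; a missing or partial stop date affects duration only.* This agrees with Sections 4.4.1.2.4 and 4.4.1.2.5. The handling of AEs whose onset is truly unknown needs no change.

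The cost is one sentence of SAP text. No new data are needed, and no programming changes if 4.4.1.2.4 is what has been coded; a check of the onset derivation in the code would confirm that.

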5.3.2 Immunogenicity

Missing data will not be imputed. No test or search for outliers will be performed.

In order to appropriately manage extreme values (undetectable responses $< \text{LLOQ}$ and $\geq \text{ULOQ}$), the following computational rule is applied to the values provided in the clinical database for each blood sample drawn for analysis purposes:

- If a value is $< \text{LLOQ}$, then use the computed value $\text{LLOQ}/2$

- If a value is between \geq LLOQ and $<$ ULOQ, then use the value
- If a value is \geq ULOQ, then use the computed value ULOQ

The derived endpoint of fold-rise is computed for extreme values, to minimize the numerator and maximizes the denominator as in [Section 4.4.2.3](#).

5.3.3 Efficacy

Not applicable

5.4 Interim / Preliminary Analysis

Due to the possibility of delayed availability of the immunogenicity data generated using rSBA in a subset of subjects, and in order to not delay the analysis of safety data and available hSBA immunogenicity data, the analysis on rSBA immunogenicity data will be done separately when all rSBA testing has been completed. No statistical adjustment will be applied as there will be no repeat analysis of the same parameter and because the rSBA immunogenicity analysis is descriptive in nature.

5.5 Determination of Sample Size and Power Calculation

[Redacted]

[Redacted]

[Redacted]

[Redacted]

[Redacted]	[Redacted]	[Redacted]	[Redacted]	[Redacted]
[Redacted]	[Redacted]	[Redacted]	[Redacted]	[Redacted]
[Redacted]	[Redacted]	[Redacted]	[Redacted]	[Redacted]
[Redacted]	[Redacted]	[Redacted]	[Redacted]	[Redacted]
[Redacted]	[Redacted]	[Redacted]	[Redacted]	[Redacted]
[Redacted]	[Redacted]	[Redacted]	[Redacted]	[Redacted]

[Redacted]

5.6 Data Review for Statistical Purposes

Review of the data has been anticipated through the data review process led by data management before database lock. This review of the data will include a statistical review.

